Participants will *utilize STAMP for 4-weeks*. As reviewed in section 5.2 (Activity 2), STAMP hosts and organizes patients' opioid/non-opioid analgesics and laxatives. It has an extensive multi-media library of education content related to pain management (approved 01/13/2020 (reference #321742)). STAMP prompts patients to take daily surveys for symptom reporting and medication updates. At the end of each survey patients receive, a summary of their symptom severity, with links to tailored educational content about pain management, and recommendations about how to safely titrate over-the-counter laxatives to manage opioid-induced constipation. This laxative advice operates within the parameters of normative and approved over-the-counter laxative use, and has been extensively reviewed, vetted, and approved by multi-disciplinary groups of clinicians. If patients report any severe symptoms, they are instructed to contact their care team immediately, with a telephone number included on the application screen, See table 6. If patients' pain is poorly controlled but not severe enough to be prompted to immediately contact their care team (for example if their average pain is above a 4 and not acceptable), they are reminded to contact their care teams if their symptoms worsen or they are concerned about it. Finally, if they report any concerning abdominal symptoms (e.g. no bowel movement in four days, haven't passed gas from bottom or ostomy, new or severe abdominal pain or vomiting two or more times), patients are not given any laxative titration instructions and are instead advised to contact their care team for more advice.

Two protocol-mandated clinician outreaches to patients will occur within a week of enrollment: 1) an RA will call to assess any technical or usability problems with the app, and 2) the nurse will review PRO's in the STAMP portal and call patients to discuss

symptoms, self-management challenges, assist patients in problem-solving, and offer medical advice. Thereafter, the RA will monitor the STAMP dashboard twice daily (Mon-Fri), and contact the patients' nurse for any symptom that is flagged as "Red" in the portal. To assist in population management, a *tiered system of color-coded flags (Red, yellow and green)* in the portal will indicate symptom severity, need for outreach and/or management changes (See Table 7). Of note, the system always prompts the patients to contact their care team for any severe symptoms and there is no expectation for proactive clinician outreach. These procedures have been approved by participating clinic nurses. Of note, nurses will also have access to this STAMP dashboard and be able to review patients' primary symptom reporting data through a personal log-in and secure password.

To minimize the burden of the intervention on clinicians, there are no automated clinician alerts (i.e. email or in-basket message) for severe symptoms, rather, patients are prompted to call their care teams or 911 (emergency services) if they report severe symptoms. Patients are reminded frequently throughout the application that the clinician portal is not monitored around the clock and therefore they should reach out for urgent needs. Symptom data are visible within the clinician portal. *Reports*, (with graphical symptom overviews, opioid use data, side effects) will be sent to oncologists ahead of scheduled clinic visits to enable effective communication, opioid titration, and other management changes.

At the end of the 4-week period, patients will be asked to complete an end of study survey [4-8 weeks]. Patients will also be invited to complete a short semi-structured interview about their experiences using the application (See Appendix AG). See below for description of the surveys.

Clinicians' involvement in the study (Cohorts B and C): Participating nurse navigators will also undergo a 30-minute tutorial in which they get oriented to the clinician portal and how to find the information about the patients (appendix AD). The RA and study nurse will undergo more extensive trainings in use of the app and study procedures, led by the primary research team. The nurse navigators will be expected to reach out to their patients enrolled in the study within a week of enrolment after reviewing the PRO's in the STAMP portal. During this call, they will discuss symptoms and self-management challenges. They may also assist patients with problem solving and offer medical advice. After the initial check-in, the nurse navigators will be asked to monitor the portal daily (Mon-Fri) and contact their patients as necessary. The RA will also be monitoring the portal and reaching out the Nurse Navigators as necessary. Nurse navigators will be asked to fill out a usability survey at the end of their involvement. Physicians will receive reports from the app prior to seeing their patients who are enrolled in the study, and they be asked for feedback after their patients completing the study. Clinicians will be asked to fill out a survey and will be invited for a 30-minute interview at the end-of-study over the phone or via Zoom. The survey can be completed remotely though a link to a Partners Healthcare compliant electronic survey system (e.g. REDCap), over the phone with the RA, over Zoom with the RA, in person with pen and paper or on a tablet.

Chart Abstraction: The study team will complete a limited structured chart abstraction at baseline and at end-of-study to collect basic non-identifiable clinical/demographic information (See appendix AF). Chart abstraction will assess clinical actions responding to STAMP data, clinicians' adherence to STAMP CDS recommendations (methods previously described);¹⁶ and healthcare utilization (e.g. hospitalization, ER visits, urgent clinic visits for symptom management.) Information collected will including the following:

- **Demographics:** Gender, age, ethnicity, race
- **Cancer:** Patient's date of diagnosis, diagnosis (cancer type), stage at diagnosis, status of active curative or palliative treatment, and history and date of surgery related to cancer, patient seen palliative care (yes/no)
- **Pain:** patient's last pain rating, type of pain, location of pain, surgeries or operations for pain, documented calls about pain.
- **Prescribed Pain Medicines:** Patient's prescribed short-acting opioid, long-acting opioid, and non-opioid pain medications, and length of time taking opioids.
- **Prescribed Laxative Medications:** Patient's prescribed laxative medications.
- **Medication side effects:** Constipation or related symptoms.
- **Clinic visits:** Unplanned or urgent clinic visits 6 months prior, during and 6 months post-intervention
- **Mental Health Diagnoses:** Whether the patient has a mental health diagnosis and what mental health diagnosis the patient has.

Monitor subjects for safety or minimize risks:

Risks to Subjects

- **Physical risks:** Physical risks to subjects include if they feel reassured by the app's feedback/content and choose not to contact their care team for severe symptoms. It is also theoretically possible that patients are given laxative titration advice that is either ineffective at relieving constipation, or results in side effective such as diarrhea or abdominal pain.
- **Psychological risks:** Reporting pain daily may be distressing for some patients.
- **Privacy risks:** There is a risk of privacy violation or loss of confidentiality; however, this is anticipated to be minimal, and the study team is committed to guaranteeing adequate protection against risk as described in the following section.

Protection Against Risks

Recruitment and Informed Consent

Participants will be sent a study letter and given the option to opt out of the study. If they do not opt out, participants will be approached in by the RA in a private and confidential manner. If the patient is eligible and interested in participation, the study letter and consent form will be reviewed with and signed by the participant. The RA will keep all

signed documents in a password protected folder or locked cabinet, accessible only to the PI-designated study team member.

In the case of remote approach, Consent forms will be sent by mail or electronically through a secure and personalized link in the FDA and HSSH compliant Mass General Brigham/Partners REDCap database. During the consent discussion, the study staff will emphasize that participation is voluntary and the participant may stop participating at any time. Consent discussions may take place over the phone or HIPAA compliant Zoom.

The informed consent to participate will adhere to strict standards regarding its content. Required sections include: Introduction; Why is this research study being done? What other options are there? What is involved in the research study? How long will I be in this research study? What are the risks or discomforts of the research study? What are the benefits of the research study? Can I stop being in the research study and what are my rights? What are the costs? What happens if I am injured or sick because I took part in this research study? What about confidentiality? Whom do I contact if I have questions about the research study?

Protection against the 3 types of risk to this study:

- Protection against physical risks: The study team has placed extensive protections against the aforementioned physical risks of the app. These protections significantly exceed the level of support and guidance that patients would receive with usual care. Moreover, patients' symptom reports will be reviewed daily by the study staff and/or nurse navigators, which represents closer monitoring than usual care. Finally, the patient-facing app always instructs patients to contact their care teams and reminds them that the portal is not monitored continuously.
 - First, the application sets a low bar for instructing patients to contact their care teams for reported symptoms. This includes reporting any new pain, fever, new or worsening back pain, new or worsening chest pain, any pain rated ≥ 8 out of a 0 to 10 scale (See table 6 for the detailed list). Moreover, if patients report moderate to severe pain levels that do not meet the previous criteria, in addition to receiving education about their pain management, they are also reminded that their care team wants to hear from them if they are concerned about their symptoms or if their symptoms are not improving. A link to their care team's number is included in the application. This level of support is much greater than what patients have usually with routine care.
 - Regarding constipation advice, our team developed algorithms that replicate typical advice given by care teams. These algorithms were generated from a rigorous development process guided by a multidisciplinary expert panel [DFCI protocol #18-662]. Furthermore, the algorithms are built off of titrating over-the-counter laxatives within the parameters of acceptable doses on the package instructions. The app will also not provide any laxative advice if the patient reports severe abdominal symptoms including not passing gas in the last 48 hours, new or severe abdominal pain, no bowel movement in 4 or more days,

vomiting 2 or more times in the past 24 hours.

- Protection against psychological risks: if in the course of their participation patients raise significant emotional distress, the appropriate care team members i.e. nurse navigator, physician, mid-level provider will be contacted to make appropriate social work or mental health referrals.

Protection against privacy risks: To monitor the risk of loss of confidentiality/privacy, the study team has ensured that the STAMP app is HIPPA compliant and meet the privacy and security standards set by DF/HCC. In addition, all collected study data will be maintained in a secure location and personal identifiers will be removed.

To maximize data security, both REDCap and STAMP employ:

User Privileges - To ensure that users have access only to data and information that they are supposed to have within the application, user privileges are utilized within the software. Each user has their own account, and their user account will only have access to information that they themselves have created or to which administrators have granted them access.

Password-protection & Authentication - Both systems are password protected and implement authentication to validate the identity of end-users that log in to the system. Auto-logout setting will automatically log a user out of the system if they have not had any activity (e.g. typing, moving the mouse) on their current web page for the set amount of time. This prevents someone else from accessing their account and their data if they leave a workstation without properly logging out or closing their browser window.

Logging and Audit Trail - Both systems maintain built-in audit trails that log all user activity and all pages viewed by every user.

What data will be collected and how:

- Study-related health information (including, demographics, cancer type, cancer stage, treatment plan, recent hospitalizations, prescription drugs) will be collected via medical record (and/or local cancer registry) review at baseline.
- Health service utilization (e.g. ED visits, hospitalizations, unplanned urgent clinic visits, changes to opioid medications) will be assessed by structured chart abstractions at end of study.
- Participant responses to the symptom reporting questions within STAMP will be collected for both use in clinical care and for research purposes.
- Data on STAMP usage by all user types will be collected.
- Patient survey at baseline and end of study
- Semi-structured patient interviews at end of study (Zoom or phone)
- Clinician survey at end of study

Measures collected via patient assessments	Survey	App data	Chart review
--	--------	----------	--------------

Assessment	Measure	T1	T2
Socio-demographics	Standard	x	
Baseline cellphone use	MTUAS ⁶⁶	x	
Pain severity/interference	BPI ⁵¹	x	x
Opioid use/adherence ¹⁹	Self-report	x	x
Quality of life	FACT-G ⁶³	x	x
Satisfaction	Novel metric		x
Use of STAMP⁵⁷	-		x
Usability	SUS ⁶⁸		x
Management changes	-		x
Healthcare utilization	-	x	x
Self-efficacy in managing symptoms	PROMIS ⁵⁴	x	x
Self-efficacy in managing medications	PROMIS ⁵⁴	x	x
Pain catastrophizing	PCS ⁶⁷	x	x
Patient reported outcomes	PRO-CTCAE ⁵³	x	x
Depression and Anxiety	PROMIS ⁵⁴	x	x
Sleep Disturbance	PROMIS ⁵⁴	x	x

Long-term study follow-up: Not applicable.

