An additional theoretical risk for participants in Cohort B is that patients may feel reassured that their symptoms are being monitored and be less likely to call their care team. We have sought to mitigate this possibility in multiple ways. First, the application has clear disclaimers that the portal is not monitored continuously, and that it should not substitute calling care teams for worrisome symptoms. Secondly, when patients report potentially serious symptoms, they are specifically instructed to notify their care team by calling or paging after hours (the clinic number is included in the application). See below for the list of symptoms that prompts phone contact:

Table 5. Severe Symptoms

Pain	
 • Worst pain = 9-10 • Worst pain = 7-10 and new pain
Red Flag Symptoms	
 • Severe weakness or fatigue • Lightheadedness or feeling like I was going to pass out • No gas or stool from my bottom (or ostomy) in the last 2 days • Vomiting 2 or more times in the last 24 hours • Fever of 100.5 or greater • New or worsening chest pain • New or worsening shortness of breath • New or worsening back pain • New numbness and weakness in one or both of your legs • Severe difficulty eating or drinking • Hallucinations/nightmares
Opioid Side Effects	
 • Hallucinations
Constipation	
 • No bowel movement in four days • Haven't passed gas from bottom or ostomy • New or severe abdominal pain • Vomiting two or more times

Severe symptom notification:

“Your care team needs to know about your symptoms. Take a break from the survey and call them [link to clinic number]. If it's after hours, ask to have your doctor paged.”

Additionally, for less severe symptoms, patients are encouraged to call their care teams if they are worried about their symptom or if it is worsening. If patients report pain that is in a moderate range of severity, or if they report that it is unacceptable to them, they are presented with the following message:

“Below, you’ll find some tips to help. Remember, your providers care about your pain. If this level of pain is not acceptable to you, or if you are worried about it, they want to hear from you. You can call them at [insert clinic number].”

Finally, the patient-facing application contains clear disclaimers on each survey that the portal is not continuously monitored, using the following language:

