Brief description of activity: A pilot study will be conducted at DFCI to demonstrate the utilization and efficacy of the STAMP app among patients with chronic cancer pain and their cancer care providers. This will be a single arm study with up to 20 patients.

Patients with advanced solid tumors who are using opioids to manage chronic cancer pain will be recruited from outpatient clinics (GCC, palliative care), and they will be asked to use the app for 4 weeks. Once a patient is enrolled in the study, a research assistant (RA) will set up the app, putting in the patient's prescribed opioids and laxatives. Patient will have access to educational materials about pain management and patient educational videos about pain management and opioids (See Appendices P, Q, and V, respectively, approved 01/13/2020 - reference #321742) through the app. Patient will be prompted to take daily surveys for symptom reporting and medication updates. At the end of each survey patients receive, a summary of their symptom severity, with links to tailored educational content about pain management, and recommendations about how to safely titrate over-the-counter laxatives to manage opioid-induced constipation. This laxative advice operates within the parameters of normative and approved over-the-counter laxative use, and has been extensively reviewed, vetted, and approved by multi-disciplinary groups of clinicians. If patients report any severe symptoms, they are instructed to contact their care team immediately, with a telephone number included on the application screen (see Table 6). If patients' pain is poorly controlled but not severe enough to be prompted to immediately contact their care team (for example if their average pain is above a 4 and not acceptable), they are reminded to contact their care teams if their symptoms worsen or they are concerned about it. Finally, if they report any concerning abdominal symptoms (e.g. no bowel movement in 4 or more days, haven't passed gas from bottom or ostomy, new or severe abdominal pain, vomiting two or more times in the past 24 hours), patients are not given any laxative titration instructions and are instead advised to contact their care team for more advice. See Table 6 for detailed information on what symptom-reports prompt patients to contact their care team immediately and to view the message as presented in the app.

[figure not shown]

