Table 6: “Red-Flag” symptoms that prompt a “call your care team” message when reported in the app

Pain	
 • Worst pain = 9-10 • Worst pain = 7-10 and new pain 	
Severe Symptoms	
 • Severe weakness or fatigue • Lightheadedness or feeling like I was going to pass out • No gas or stool from my bottom (or ostomy) in the last 2 days • Vomiting 2 or more times in the last 24 hours • Fever of 100.5 or greater 	

PROTOCOL TITLE: *Smartphone Technology to Alleviate Malignant Pain (STAMP)*

Version 8, November 23, 2021

	
 • New or worsening chest pain • New or worsening shortness of breath • New or worsening back pain • New numbness and weakness in one or both of your legs • Severe difficulty eating or drinking • Hallucinations/nightmares 	
Opioid Side Effects	
 • Hallucinations 	
Constipation	
 • No bowel movement in four days • Haven't passed gas from bottom or ostomy • New or severe abdominal pain • Vomiting two or more times 	

The research team will monitor the portal where patient survey responses are presented. If a severe symptom is reported, the research team will contact the relevant nursing staff for clinical follow-up (as per the above paragraph, patients are always advised to contact their care teams for safety concerns, and there is no expectation for immediate nurse outreach). Nurses and physicians involved in the care of participating patients will also have access to patient-responses on the clinician portal. Patients will complete measures for their pain management, mood and barriers to pain management at baseline and at the

end of-study (see appendices AE and AI, respectively). An end-of-study semi-structured interview will assess adherence to STAMP's self-management recommendations, perceived usefulness of STAMP and its impact on care team interactions (see appendix AG for interview guide).

There will be a maximum of three attempts to contact the patient. During each attempt, the patient will be called, and if there is no response, a voicemail will be left [See Appendix AL for phone call and voicemail scripts]. Patients will be considered opted-out of the study if they do not respond to the maximum of 3 attempted contacts, or if they indicate that they would like to opt-out of the study during the call or their reply to the voicemail.

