14.0 Provisions to Monitor the Data to Ensure the Safety of Subjects*

This is a social behavioral research project, not a treatment protocol. The study involves questionnaire-based assessments and symptom reporting and monitoring. As such, the only adverse event that will be monitored and reported is psychological distress as determined by the treating oncologist. For any patient who exhibits severe distress as result of the study procedures, the study research assistant will notify the patients' oncologist and social worker for appropriate response, including possible mental health referral if necessary. Furthermore, participants will be reminded that participation is voluntary and can be stopped at any time for any reason. See the DSMP (appendix F) for more details.

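### Section 5.4 states the app's contact-your-team pain trigger more widely than Table 6, which it cites, and Section 14 leaves the app's named physical risks out of adverse-event reporting

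*Combined protocol and SAP*

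**What the plan says.** **Trigger.** In Section 5.4, Protection Against Risks, the first safeguard against physical risk is a low threshold for telling patients to contact their team: "This includes reporting any new pain, fever, new or worsening back pain, new or worsening chest pain, any pain rated" at or above "8 out of a 0 to 10 scale (See table 6 for the detailed list". The brief description of Activity 4 also defers to that table: "See Table 6 for detailed information on what symptom-reports prompt patients to contact their care team immediately". Table 6, whose title describes symptoms that produce the contact "message when reported in the app", has two pain lines: "Worst pain = 9-10" and "Worst pain = 7-10 and new pain". Table 5 in Section 5.3 gives the same two lines. Table 6 also lists new or worsening back pain, new or worsening chest pain, and new or severe abdominal pain separately. Below the trigger, poorly controlled pain that is "not severe enough to be prompted to immediately contact their care team (for example if their average pain is above a 4 and not acceptable") receives a softer reminder.

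**Safety reporting.** Section 5.4, Risks to Subjects, names two physical risks. A patient may be reassured by the app and not call about severe symptoms. The laxative advice may also fail, or cause diarrhea or abdominal pain. Section 14 says that "the only adverse event that will be monitored and reported is psychological distress as determined by the treating oncologist", and refers to the DSMP (Appendix F) for detail. For the pilot, Section 10 lists alert counts, the proportion of alerts leading to clinical action, medication changes and symptom trajectories, all as exploratory.

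**The concern.** The trigger sentence is offered as protection against the false-reassurance risk. Anyone assessing that risk from the narrative would believe the app tells patients to call in situations where the operative list does not. The cut-off is specific (8 against 9) and the severity floor on new pain is dropped, so loose paraphrase does not explain the difference.

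The second part concerns what the pilot will report. The app gives laxative titration advice, and the protocol itself names the harms this could cause. Section 14 does more than stay silent on them: the word only excludes them. The pilot is meant to refine the app and support an application for a randomized trial. Followed as written, the plan would reach that stage with no summary of laxative-related harms, although much of the relevant data is already being collected.

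**Working it through.** **1. The two trigger rules.** Let w be the worst-pain score (0-10). Reading the narrative's pain rating as worst pain is an assumption. Reading it as average or current pain would not reproduce Table 6 either, because Table 6 uses only worst pain and newness.

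- Section 5.4 narrative: message if w ≥ 8, or if the pain is new.
- Table 6: message if w ≥ 9, or if w ≥ 7 and the pain is new.

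The enumeration leaves out new pain scored 0 and pain caught by the separate back, chest and abdominal items.

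| Reports | Narrative fires | Table 6 fires | Differ |
|---|---|---|---|
| Non-new, 0-10 (11) | 8, 9, 10: 3 | 9, 10: 2 | 8 |
| New, 1-10 (10) | 1-10: 10 | 7-10: 4 | 1-6 |
| Total (21) | 3 + 10 = 13 | 2 + 4 = 6 | 1 + 6 = 7 |

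Every combination that fires under Table 6 also fires under the narrative, so all 7 differences overstate the protection (13 − 6 = 7). The count gives each combination equal weight, and the documents do not say how often any of them occurs.

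**2. What happens to those 7 reports.** Section 5.4 has the research assistant check the dashboard twice daily, Monday to Friday, and contact the nurse for any symptom flagged Red. The sample pain grids in Section 5.2 (Table 1) suggest which reports would be Red. Their axes are unlabelled. Cells with column above row are mostly marked as nonsensical, which suggests rows are worst pain and columns average pain. On that reading:

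- Pain not acceptable: every valid cell in rows 4-8 is Red. This covers non-new 8 and new 4-6, which is 4 of the 7. New 1-3 is Yellow.
- Pain acceptable: row 8 is Red only at columns 7-8. Rows 1-6 are Green or Yellow.

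So some of the 7 would still lead to staff contact on weekdays. This depends on a table described as a sample, and on its Red matching the portal's Red.

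**3. Named physical risks against planned reporting.**

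| Risk named in 5.4 | Adverse event in Section 14 | Related item in Section 10 |
|---|---|---|
| False reassurance | No | Proportion of alerts with clinical action (exploratory) |
| Laxative advice ineffective or harmful | No | Alert counts and symptom trajectories (exploratory); no summary of harms |

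Data that could be tabulated are already planned. There are daily app reports. PRO-CTCAE is given at baseline and end of study. Chart abstraction covers constipation or related symptoms, ER visits, hospitalizations and urgent visits.

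**4. What a table could show with 20 patients.** Exact (Clopper-Pearson) 95% limits:

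- 0 of 20: upper limit = 1 − 0.025^(1/20) = 16.8%.
- 2 of 20: 1.2% to 31.7%.

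Such a table is descriptive only. It could not establish that the laxative advice is safe.

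**The case against.** **The trigger error sits in a narrative, and the operative rule is consistent.** Tables 5 and 6 agree, and the narrative itself defers to Table 6. A programmer or nurse working from the tables would not be misled. This stands, and it is why the point is minor. The sentence still needs correcting, because it describes a safeguard that the cited table does not provide.

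**A reader might infer that patients in the gap get no response.** The documents do not support that. Many would see the softer reminder, and step 2 shows that some would be Red and passed to a nurse. The overstatement concerns the message shown to the patient. Nor do the documents show that the app is programmed wrongly, since the programmed rule is not given.

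**A reader might infer that the physical risks go unmonitored.** That is also unsupported. Section 11 says safety monitoring varies by activity and points to Section 5. The pilot has daily symptom review, research-assistant-to-nurse contact and a nurse call within a week of enrollment. Last bowel movement and severe symptoms appear on the dashboard. Laxative doses stay within package limits, advice is withheld for abdominal red flags, and recurrent bowel obstruction is an exclusion. What is missing is designation as reportable events and a summary of them. The DSMP may say more, but any wider list there would conflict with the word only in Section 14.

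**Constipation would mostly be background.** The Background section describes opioid constipation as nearly universal. In a single arm of 20, recording it as an adverse event would say little about the app. This stands, and the fix treats it as a symptom outcome.

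**Recording who initiated contact does not measure false reassurance.** This also stands: early staff outreach can pre-empt a patient's call. It is not negligible work either, since alerts could arise from up to 20 × 28 = 560 daily surveys.

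**Conclusion.** Both parts hold, with limited consequence.

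1. **Minor; wrong as written.** The Section 5.4 narrative is wider than Table 6 for non-new worst pain of 8, and for new pain of 1-6 outside the back, chest and abdominal triggers. That is 7 of 21 combinations, all in the direction of overstating the patient-facing protection. It rests on reading the narrative's rating as worst pain. Portal follow-up reduces the practical effect by an amount that cannot be estimated from the documents.

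2. **Cheap improvement.** Neither of the two physical risks named in Section 5.4 is within Section 14's adverse-event scope, and Section 10 plans no summary of laxative-related harms. This is established for the protocol text only; the DSMP and the survey and abstraction forms were not available.

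The primary feasibility and acceptability outcomes are not affected by either part.

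**What to change.** **Trigger.** Check the programmed rule first. If it matches Table 6, change the Section 5.4 narrative to: worst pain 9-10, or worst pain 7-10 that is new. If the app follows the narrative, correct Tables 5 and 6 instead.

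**Section 14** (and the DSMP, if it says the same). Alongside psychological distress, list diarrhea and new or severe abdominal pain after app laxative advice, and related ER visits or hospitalizations, during the 4-week app period.

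**Section 10.** Tabulate the number and proportion of patients with each event, descriptively and without attribution to the app, from the app, PRO-CTCAE and chart data already collected. The end-of-study survey may be completed as late as week 8, so app and chart data should define the 4-week window. Report persistent constipation as a symptom outcome, not an adverse event. Add a diarrhea item only if the existing surveys lack one.

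**Optional.** Record who initiated contact after each severe-symptom alert, and state that this does not by itself measure false reassurance.

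**Cost.** One corrected sentence (or two table entries), a longer list in Section 14, one descriptive table, and slightly more event recording.
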